# **Endpoints** (efficacy, safety)

### Primary Objective Endpoint:

 Proportion of patients with NFPA reaching tumor volume decrease of at least 20% after the 24-week treatment with pasireotide LAR.

#### **Secondary Objectives Outcomes:**

- Mean tumor volume change evaluated by pituitary MRI between baseline and weeks 4, 12, 24, 48, 72, and 96.
- Percent tumor volume change evaluated by pituitary MRI between baseline and weeks 4, 12, 24, 48, 72, and 96.
- Proportion of patients reaching tumor volume decrease of at least ≥ 20% after 4, 12, 48, 72, and 96 treatment weeks.
- Time to treatment response for treatment responders, defined as the time from the first injection to the first evaluation in which the patient reached a tumor volume decrease of at least ≥ 20%.
- Change in the grading score for disease-related symptoms between baseline and weeks 4, 12, 24, 48, 72, and 96.
- Incidence of pituitary hormone dysfunction on baseline and weeks 4, 12, 24, 48, 72, and 96.
- Proportion of patients reaching alpha subunit decrease of at least 50% on weeks 4, 12, 24, 48, 72, and 96.
- Proportion of patients reaching alpha subunit normalization on weeks 4, 12, 24, 48, 72, and 96.
- Percentage of adverse events with CTC grade ≥ 3 during treatment with pasireotide LAR.
- Percentage of patients with at least one adverse event with CTC grade ≥ 3.
- Incidence of all adverse events, incidence of abnormal laboratory values, and summary of laboratory evaluations.
- For the extension phase: among patients considered as responders (i.e., patients reaching a tumor volume decrease of at least 20% compared to the initial tumor volume), evaluate the number and proportion of patients remaining responsive throughout the extension phase treatment period (according to magnetic resonance imaging evaluations on weeks 48, 72, and 96).
- To evaluate the percentage of patients remaining with stable tumor volume throughout the study, i.e., patients mantaining a tumor volume variation of less than 20% in relation to baseline tumor volume (according to magnetic resonance imaging evaluations on weeks 24, 48, 72, and 96).

Study design	A Phase II, open-label, single-arm, prospective, multicenter study to evaluate the efficacy and safety of pasireotide LAR 60 mg in adult patients with NFPA.				
	Main Phase: During the main phase of the study, visits will be performed every 28 ± 3 days, with 2 extra safety visits on days 20 and 76. For all evaluations and visits of the Main Phase, see Table 7-1.				
	Eligible patients will receive pasireotide LAR 60 mg every 28 ± 3 days for 24 weeks, during the Main Phase of the study. Dose decreases to 40 mg will be allowed, due to safety issues. In case of rapid deterioration of the visual field or sudden visual loss, the patient will be discontinued from the study.				
	Extension Phase: After the main phase of the study (first 24 weeks of treatment), patients who have derived benefit from treatment with pasireotide LAR, according to the evaluation by the physician in charge, will be offered the opportunity to enter the Extension Phase. Patients will continue to receive pasireotide LAR in 4-week intervals for up to 92 weeks or until pasireotide or other effective therapy becomes commercially available or until clinical benefit is no longer noticed (whichever occurs first).  For all evaluations and visits in the Extension Phase, see Table 7-2.				
Population	The population for this study is composed of adults diagnosed with NFPA who did not receive previous therapy (treatment-naïve) for the disease. Due to the difficulty to evaluate changes in tumor volume in microadenomas, and also because they may be mistakenly diagnosed as incidentalomas, only patients with macroadenomas (≥ 1 cm) may be enrolled in the study.				
Inclusion / exclusion criteria	
 
Inclusion:         
 
Male and female patients ≥ 18 years old
 
Patients with clinically non-functioning pituitary macroadenomas ≥ 1 cm
 
No previous treatment for NFPA
 
Eastern Cooperative Oncology Group (ECOG) Performance status (PS) of 0 to 1
 
Written Informed Consent Form obtained before any screening procedure
 
 
 
Exclusion:         
 
Patients requiring surgical intervention for relief of any sign or symptom related to tumor compression
 
 
 
				

- Previous pituitary surgery
- Previous medical treatment for pituitary tumor
- Patients who received pituitary radiation within 10 years previous to the enrollment visit (visit 2)
- Prolactin (PRL) levels > 100 ng/mL (PRL evaluation must be performed with diluted samples in order to ensure prevention of the "hook effect")
- Patients with optic chiasm compression, causing clinically significant acute defects on visual field
- Diabetic patients whose blood glucose is poorly controlled, as confirmed by HbA1C > 8%
- Patients with known gallblader or bile duct disease, acute or chronic pancreatitis (patients with asymptomatic cholelithiasis and asymptomatic dilation of the bile duct may be enrolled)
- Patients with abnormal coagulation (increased PT or APTT 30% above normal limits) or patients who received anticoagulants affecting PT (prothrombin time) or APTT (active partial thromboplastin time)
- Patients experiencing congestive heart failure (NYHA Class III or IV), unstable angina, persistent ventricular tachycardia, ventricular fibrillation, advanced heart blockade, or history of acute myocardial infarction within 24 weeks previous to the enrollment visit (visit 2)
- Screening (Visit 1) or baseline (pre-dose, visit 2) QTcF > 450 msec
- Patients with history of syncope or family history of sudden idiopathic death
- Patients with persistent or clinically significant cardiac arrhythmias
- Patients with Torsades de Pointes risk factors, such as uncorrected hypopotassemia, uncorrected hypomagnesemia, heart failure, clinically significant / symptomatic bradycardia, or high degree AV block
- Patients with concurrent disease(s) that may prolong QT interval, such as autonomous neuropathy (caused by diabetes or Parkinson's disease), HIV, cirrhosis, uncontrolled hypothyroidism, or heart failure
- Patients taking medication(s) known to prolong QT interval
- Patients with liver disease or history of liver disease, such as cirrhosis, chronic active hepatitis B and C or persistent chronic hepatitis, or patients with ALT and/or AST > 2 x ULN, total blood bilirubin >1.5 x ULN, and blood albumin < 0.67 x LLN

- Patients with WBC count < 3x 10^9/L; Hgb < 90% LLN; platelets < 100x 10^9/l
- Patients with any current or previous medical condition that, in the investigator's opinion, may interfere with the conduction of the study or the evaluation of the study results
- Patients with history of immunological impairment, including a positive result for HIV tests (ELISA and Western blot). An HIV test will not be required; however, previous medical history will be analyzed
- Patients with known hypersensitivity to somatostatin analogues or any other pasireotide LAR component
- Patients with active malignant disease within the last five years (except for basal cell carcinoma or in situ cervix carcinoma)
- Patients with presence of uncontrolled, acute suspected, or active chronic infection

	
 
Pregnant or breastfeeding patients, or patients of childbearing potential, who do not adopt a clinically acceptable contraceptive method. If a woman is participating in the study, then a contraceptive method will be sufficient (pill or diaphragm), and the male partner must use condoms. If an oral contraceptive is used in addition to condoms, the patient must have adopted this method for at least 2 months prior to enrollment in the study, and must agree to continue to use the oral contraceptive throughout the study, and for three months after the end of the study. Sexually active male patients are required to use condoms throughout the study and for three months after the end of the study, as a precautionary measure (available data do not suggest any increase in reproductive risk with the study drugs)
 
Study participants on an investigational drug 30 days before the enrollment visit (visit 2). Patients must have recovered from all side effects from other investigational therapies.
 
Patients with history of non-compliance to medical treatments, patients considered non-compliant, or any circumstance at the time of enrollment in the study that might prevent the completion of the entire study or required follow-up
 
Patients experiencing improper use/abuse of alcohol or drugs, in the past or currently, within 12 months before visit 1 (screening)
 
Presence of Hepatitis B surface antigen (HBs-Ag)
 
Presence of antibody screen for Hepatitis C (anti-HCV)
 
Patients undergoing major surgery / surgical therapy for any cause within 4 weeks before randomization
 
Patients with confirmed hypothyroidism, hypoadrenalism, and hypogonadism (except physiological andropause and menopause), unless properly treated with stable doses of hormone replacement therapy for at least 3 months before study entry
 
Patients with uncontrolled cardiovascular, renal, or metabolic disorders
 
Patients with contraindication to MRI, such as, for example (but not limited to):

Patient numbering	Each study patient is uniquely identified by a 6-digit patient number, which is a combination of the 3-digit site number and the 3-digit subject number.
Investigational and control drugs	Depot IM pasireotide LAR (long-acting release) injection. (Pasireotide LAR excipients include: mannitol, sodium carmellose (sodium carboxymethyl cellulose), poloxamer 188, and water for injection).
Control drug	Not applicable
Dose, schedule, treatment cycle	Main Phase: The study drug is pasireotide LAR at a 60 mg dose every 28 ± 3 days, for 6 months, administered as intragluteal depot IM injection by the clinical staff or healthcare professional at each research site. The first 60 mg dose of IM pasireotide LAR will be administered on Visit 2, after all baseline evaluations are completed and the eligibility to participate in the study is confirmed. For patients unable to tolerate the dosage schedule specified in

the protocol, a dose decrease to 40 mg is allowed. Patients unable to tolerate the minimum pasireotide LAR dose of 40 mg will be discontinued from the study.

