Hypopituitarism may occur in pituitary macroadenomas as a result of (a) compression of the pituitary stalk, leading to a decrease of hypothalamic hormones reaching the pituitary gland; (b) compression of the normal pituitary tissue; and (3) hypothalamic involvement of the pituitary tumor (Dekkers et al 2008). The hypogonadism seen with these adenomas is frequently associated to the increase in blood prolactin levels (usually < 200 ng/mL) (Jaffe 2006). Patients with hypopituitarism are at increased risk of mortality due to cardiovascular, cerebrovascular, and/or respiratory disease (Bates et al. 1996)(Rosen et al. 1990)(Bulow et al 1997)(Nilsson et al 2000)(Tomlinson et al 2001).

Hypopituitarism due to NFPA may produce different symptoms. Four out of five patients with NFPA experience secondary hypothyroidism, and 3 out of 5 experience secondary adrenal failure (Jaffe 2006). Most patients also experience signs and symptoms of hypogonadism, frequently as a result of direct compression by a large adenoma and growth hormone (GH) deficiency (Jaffe 2006). Approximately 60% to 80% of patients experience visual field defects, a consequence of tumor pressure on the optic chiasm (Jaffe 2006)(Dekkers et al 2007). In some cases, these tumors compress other surrounding brain tissues and lead to dysfunctions in the cranial nerves (Jaffe 2006)(Vance 2008). Frequently, patients experience headache, although this event is not diagnosed (Vance 2008).

The evaluation of the tumor volume and location of the pituitary adenoma are performed more efficiently by magnetic resonance imaging (MRI) (Dekkers et al 2008). Screening hormone tests that may determine pituitary deficiency include ACTH, cortisol, TSH, free thyroxin (T4), insulin-like growth factor I (IGF-1), luteinizing hormone (LH), follicle-stimulating hormone (FSH), and testosterone (in men) (Vance 2008). Prolactin is also useful for diagnosis, but it must be diluted if the patient presents a large lesion, in order to avoid the "hook effect" and a possible mistaken diagnosis (Vance 2008) (the hook effect may be defined as falsely low values in an immunoassay when an extremely large amount of antigens affects the binding ability of the antibody added).

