# 3.2 Secondary objectives

- To evaluate the effect of pasireotide LAR in mean tumor volume variation between baseline and treatment weeks 4, 12, 24, 48, 72, and 96.
- To evaluate the effect of pasireotide LAR in mean percent tumor volume variation between baseline and treatment weeks 4, 12, 24, 48, 72, and 96.
- To evaluate the effect of pasireotide LAR in the proportion of patients reaching tumor volume decrease of at least  $\geq 20\%$  after 4, 12, 48, 72, and 96 weeks of treatment.
- To evaluate the effect of pasireotide LAR on time to tumor response.
- To evaluate the effect of pasireotide LAR on the disease-related symptoms \*
   \* Disease-related symptoms to be evaluated: headache, visual disorders, fatigue, decreased libido, erectile dysfunction (for men only), menstrual irregulative or interruption (only for non-menopausal women).
- To evaluate the effect of pasireotide LAR on the pituitary function on weeks 4, 12, 24, 48, 72, and 96.
- To evaluate the effect of pasireotide LAR on the alpha subunit levels on weeks 4, 12, 24, 48, 72, and 96.
- To evaluate the overall safety and tolerability of pasireotide LAR.
- For the extension phase: duration of response for patients considered as responders (i.e., patients reaching a tumor volume decrease of at least 20% compared to the initial tumor volume).
- To evaluate the percentage of patients remaining with stable tumor volume during the study.

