- 29. Presence of Hepatitis B surface antigen (HBsAg).
- 30. Presence of Hepatitis C antibody screen (anti-HCV).
- 31. Patients who had a major surgery / surgical therapy for any cause within 4 weeks before randomization.
- 32. Patients with confirmed hypothyroidism, hypoadrenalism and hypogonadism (except for physiological andropause and menopause), unless appropriately treated with stable doses of hormone replacement therapy for at least 3 months before study entry.
- 33. Patients on growth hormone replacement therapy.
- 34. Patients with uncontrolled cardiovascular, renal or metabolic disorders.
- 35. Patients with severe neurological or psychiatric disorders.
- 36. Patients with contraindications to MRI such as, for example, (but not limited to): brain aneurysm clips, internal wiring of cardiac pacemaker and temporary pacemaker, cochlear implants, hearing devices containing internal non-removable parts, Swan-Ganz catheter, aortic balloon, Endovascular Graft Zenith AAA, and other potential contraindications related to ferromagnetic materials identified in the patient's interview.

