#### 6.4.3 Other concurrent medication

The investigator must instruct patients to notify the study site about any new medication administered after starting the study drug. All medications (except the study drug) and significant non-drug therapies (including physical therapy and blood transfusions) administered after the patient starts treatment with the study drug must be mentioned in the Concurrent Medication / Significant non-drug therapy eCRF after the study drug is started. If possible, there may be no changes in any concurrent medication during the study until all EOS evaluations are completed.

The use of anticoagulant medication should be avoided.

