# 7.4.2 Secondary efficacy evaluations

Tumor volume will also be evaluated as described on Section 7.4.1. Time to response will also be obtained (i.e., time to reach tumor volume decrease  $\geq 20\%$ ).

Disease-related symptoms will be reported by patients and recorded by the medical staff, on all Main Phase visits and on visits 13 (week 36), 16 (week 48), 19 (week 60), 22 (week 72), 25 (week 84), and 28 (week 96) of the Extension Phase.

Disease-related symptoms to be evaluated: headache, visual disorders, fatigue, decreased libido. Only for men: erectile dysfunction. Only for non-menopausal women: irregular or interrupted menstrual cycles. The investigator will also ask patients to classify the symptoms above according to a 5-point scale (0 = absent, 1 = mild, 2 = moderate, 3 = severe, 4 = very severe). The remaider will be evaluated as absent or present.

Hormone profiles, including growth hormone (GH), insulin-like growth factor I (IGF-1), follicle-stimulating hormone (FSH), luteinizing hormone (LH), adrenocorticotropic hormone (ACTH), thyroid-stimulating hormone (TSH), prolactin (PRL), cortisol, free T4, and estradiol (for women) or testosterone (for men), will be evaluated in the Screening Period (and will be considered as baseline data) and on Weeks 4, 12, and 24 of the Main Phase. Evaluations in the Extension Phase will be performed on Weeks 48, 72, and 96.

Alpha subunit levels will be measured in the Screening Period (and will be considered as baseline data), on Weeks 4, 12, and 24 in the Main Phase, and on Weeks 48, 72, and 96 in the Extension Phase.

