n(%)	. ,									
Yes										
No										
Total										
Improved, n (%)										
Yes										
95%CI										
No										
Total										

Table 10 (Cont.) – Disease-related symptoms – FAS population

	Total (n=xx)									
	V1	V2	V3	V4	V5	V6	V7	V8	V9	V10
Regular menses ^{c)} ,	n									
(%)										
Yes										
No										
Total										
mproved, n (%)										
Yes										
95%CI										
No										
Total										

a) For each symptom, it will considered as improvement if the severity reduce at least one point (eg. 'Severe' at v₁ and 'moderate' at v₁ will be considered as improvement in vi).

b) For patients who registered 'No' in V₁ and 'Yes' in v_i it will be considered as an improvement in v_i.

c) For patients who registered 'No' in V₁ and 'Yes' in v_i it will be considered as an improvement in v_i.

Table 11 (Cont.) – Alpha-subunit – FAS population

	Total (n=xx)					
	V1	V4	V7	95%CI	V10	95%CI
α subunit (ng/mL)						
N				-		-
Mean				-		-
Median				-		-
Standard Deviation				-		-
Minimum				-		-
Maximum				-		-
Normal				-		-
Abnormal				-		-
CS				-		-
NCS				-		-
Reduction of α subunit ≥50% ^{c)} , n (%)						
Yes						
No						
Total						

CS: Clinically significant; NCS: Not clinically significant. 95%CI: 95% confidence interval.

c) For reduction ≥50%='yes' will be considered all patients who obtained percentage change from baseline in α subunit at visit i' ≥50.

Table 13 – Visual field – FAS population

	Total							
	(n=xx)							
	V1	V2	V4	V5	V7	V8	V9	V10
Right eye								
Normal/abnormal, n (%)								
Normal								
Abnormal								
Mild								
Severe								
Total								
Findings, n (%)								
Upper right quadrantanopia								
Upper left quadrantanopia								
Lower right quadrantanopia								
Lower left quadrantanopia								
Temporal hemianopsia								
Nasal hemianopsia								
Other								
Evolutive information, n (%)								
Stable								
Improved								
Worsened								
Total								
Left eye								
Normal/abnormal, n (%)								
Normal								
Abnormal								
Mild								
Severe								
Total								
Findings, n (%)								
Upper right quadrantanopia								
Upper left quadrantanopia								
Lower right quadrantanopia								
Lower left quadrantanopia								
Temporal hemianopsia								
Nasal hemianopsia								
Other								

Table 13 (Cont.) – Visual field – FAS population

	Total (n=xx)							
	V1	V2	V4	V5	V7	V8	V 9	V10
Left eye Evolutive information, n (%) Stable Improved Worsened Total								

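### The SAP counts a fall in fatigue or headache, or a return to regular menses, as improvement even when another treatment of that symptom was started or increased on study

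*Protocol*

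**What the plan says.** **Entry.** The synopsis admits patients with confirmed hypothyroidism, hypoadrenalism or hypogonadism only if they are on stable replacement: "unless properly treated with stable doses of hormone replacement therapy for at least 3 months before study entry". Exclusion 32 in Protocol 5.2 says the same: "unless appropriately treated with stable doses of hormone replacement therapy for at least 3 months before study entry". Neither text covers the time after entry.

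**On study.** Protocol 6.4.3 says: "If possible, there may be no changes in any concurrent medication during the study until all EOS evaluations are completed". It also expects new drugs and has them recorded: "The investigator must instruct patients to notify the study site about any new medication administered after starting the study drug". It states no consequence for the analysis if medication changes.

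**Objective.** Protocol 3.2 lists as a secondary objective: "To evaluate the effect of pasireotide LAR on the disease-related symptoms". The trial has one arm. Protocol 7.4.2 names the symptoms: "Disease-related symptoms to be evaluated: headache, visual disorders, fatigue, decreased libido", plus erectile dysfunction in men and irregular or interrupted cycles in non-menopausal women.

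**Scoring.** Under footnote a of SAP Table 10, which applies to headache, visual disturbances and fatigue, "it will considered as improvement if the severity reduce at least one point", measured from V1. Footnote c counts menses that go from not regular at V1 to regular as improved. Table B 5 repeats these definitions for the extension. SAP 5.5.1 asks for the frequency and percentage improved at each time point with an exact 95% CI. No definition refers to concurrent treatment.

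**The concern.** Fatigue can respond to thyroid or adrenal replacement, menses to sex-hormone replacement, and headache to an analgesic. A patient who starts or increases one of these after V1 and then scores a point lower, or becomes regular, is counted as improved. There is no control arm in which the same changes would also occur, so the improvement percentage combines any drug effect with the effect of the added therapy. For these symptoms the error favors the drug. A reader of Table 10 could not tell the two apart, because no table shows who had therapy added, or when. The point concerns the symptom counts, not the hormone values.

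**Working it through.** **1. Is there a rule elsewhere that handles added therapy?**

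| Place | What it covers | Added symptom therapy? |
|---|---|---|
| Protocol 10.5.1, SAP 5.5.1 | Symptom summaries, change from baseline, percentage improved | No exclusion, flag or sensitivity analysis |
| SAP 5.4.3 | Missing values and discontinuations; data as observed | Not mentioned |
| SAP Table 4 | Yes/no count of medication for hormone replacement | No timing, no link to symptoms |
| SAP Table B 2 | Yes/no count of any medication in the extension | No replacement row |
| SAP Tables 30 and B 23 | Cortisol limited to patients not taking glucocorticoid | Hormone values only |
| SAP Table 31 | Hormone levels by replacement status | V1 only, hormone values only |

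The SAP takes replacement into account when it reads hormone values but not when it reads symptoms.

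**2. Which rows can be inflated as written?**

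- Fatigue: graded from absent to very severe, footnote a. Yes.
- Headache: same grading. Yes, through other treatment such as analgesics.
- Regular menses: No to Yes counts as improved, footnote c. Yes.
- Erectile dysfunction: scored Yes/No, and footnote b counts No at V1 to Yes later as improved. A man whose dysfunction resolves goes from Yes to No and is not counted. Not inflated by this route.
- Decreased libido: no row in Table 10 or Table B 5, so there is no rate to inflate.

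**3. Interval method.** The plan gives no figure for symptoms, so I checked the method against SAP Table A 4. For x of n and confidence 1 − α, the exact limits are:

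- lower = the α/2 quantile of Beta(x, n − x + 1), or 0 if x = 0
- upper = the 1 − α/2 quantile of Beta(x + 1, n − x)

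With x = 3, n = 19 and α = 0.10 this gives 4.4% to 35.9%, as printed. The other rows of Table A 4 also reproduce.

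**4. Illustration at the SAP's 95% level for symptoms.** Inputs: n = 23 enrolled (Protocol 10.6). The number of patients who improve in fatigue only after added replacement is **assumed**, and no other patient improves.

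| Assumed number | As-observed rate | Exact 95% CI |
|---|---|---|
| 1 | 1/23 = 4.3% | 0.1% to 21.9% |
| 2 | 2/23 = 8.7% | 1.1% to 28.0% |
| 3 | 3/23 = 13.0% | 2.8% to 33.6% |

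If these patients are not counted, the rate is 0/23 = 0%, with upper limit 1 − 0.025^(1/23) = 14.8%.

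**5. The same with other improvers present.** Take 19 evaluable patients and assume 6 improve: 31.6% (95% CI 12.6% to 56.6%). If 1, 2 or 3 of the 6 had therapy added, the rate without them is 5/19 = 26.3% (9.1% to 51.2%), 4/19 = 21.1% (6.1% to 45.6%) or 3/19 = 15.8% (3.4% to 39.6%).

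**The case against.** **The endpoint is descriptive.** It is secondary, in a proof-of-concept study, with no test attached, and counting patients as observed is a legitimate choice. That stands, and it is why the as-observed row should stay. It does not remove the need to show how much of that row followed added therapy when the objective speaks of a drug effect.

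**Screening should make starts uncommon.** Exclusion 32 removes confirmed deficiency that is not stably treated, and hormones are measured at screening. A deficiency that arises on study and is then replaced would tend to bring the patient back to the V1 level, which is not improvement. This stands as a limit on size: the mechanism needs a deficit missed or undertreated at V1, or a symptom treated for another reason. It does not close the gap.

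**Stronger readings that the documents do not support:**

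- A reader might infer that men who start testosterone will inflate the erectile or libido rates. As written they cannot, for the reasons in step 2 of the working. Footnote b looks reversed, and if it is corrected the erectile row becomes exposed in the same way.
- A reader might infer that on-study starts are to be expected, because Protocol 1.1 says: "Most patients also experience signs and symptoms of hypogonadism, frequently as a result of direct compression by a large adenoma". That text describes NFPA patients in general, not the screened population.
- A reader might infer that changes are freer in the extension, because the request in 6.4.3 ends at the EOS evaluations. Table 7-2 also labels Visit 28 as EOS, so the request may run to week 96.

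**A stricter count has its own error.** A patient who improved before the therapy was added would also be lost from it. That is correct and is a reason to show both counts.

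**Conclusion.** The concern holds in a limited form. The SAP's definition credits as improvement any one-point fall in fatigue or headache, and any change to regular menses, that follows added therapy. The protocol discourages such additions but does not rule them out. For these symptoms the bias favors the drug. Its size cannot be derived from the documents, since they give no count of on-study starts or increases. The 13.0% against 0% contrast rests on an assumed 3 of 23 patients; each such patient adds 1/23 = 4.3 percentage points. The primary endpoint and the sample size rest on tumor volume and do not change. The change should be made before the symptom tables are produced, but it does not threaten the trial's main result.

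**What to change.** In SAP 5.5.1 and Tables 10 and B 5:

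- Keep the present improvement row as observed.
- Add a second row in which a patient counts as not improved at visit i if hormone replacement, or a listed direct treatment of that symptom, was started or increased after V1 and before visit i. Start the flag at V1, because improvement is measured from V1. Every patient stays in the denominator.
- List the qualifying treatments for each symptom in advance, so that, for example, the handling of a single analgesic dose for headache is settled beforehand.
- Give the exact 95% CI for both rows in Table 10. Table B 5 has no interval row at present.
- Base any statement about an effect of pasireotide on symptoms on the second row.

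In Tables 4 and B 2, add a row for replacement started or increased on study. First confirm that the Concurrent Medication eCRF captures start dates and dose-change dates; Protocol 6.4.3 requires the medications to be entered but does not say that these dates are.

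The cost is SAP wording, one derived flag and a few table rows, provided those dates are captured. The second row will be somewhat lower and conservative, since patients who improved before the added therapy also leave it. This changes the analysis only; no rule on replacement treatment itself is proposed.
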